## 4.1. Inclusion Criteria

Each potential subject must satisfy all of the following criteria to be enrolled in the study.

- 1. The ability to understand and sign a written ICF, which must be obtained prior to initiation of study procedures.
- 2. Currently being treated with a stable ARV regimen consisting of a bPI (limited to DRV once daily with rtv or COBI, ATV with rtv or COBI, or LPV with rtv) combined with FTC/TDF only, for at least 6 consecutive months preceding the screening visit.

Subjects treated with the combination DRV + COBI + FTC/TDF and having completed the required visits in the GS-US-216-0130 study, and who are fulfilling the present protocol criteria, will be given the option to participate in this study.

Note: A change in pharmacokinetic booster (ie, rtv or COBI) will be allowed provided such a switch occurred no less than 1 month prior to the screening visit.

- 3. Documented evidence of being virologically suppressed while on a stable ARV regimen prior to screening: at least 1 plasma HIV-1 RNA measurement <50 copies/mL (or HIV-1 RNA undetectable by a local HIV-1 RNA test) occurring between 12 and 2 months prior to the screening visit while on the stable ARV regimen and have HIV-1 RNA <50 copies/mL at the screening visit.
  - A single viral load elevation of ≥50 copies/mL and <200 HIV-1 RNA copies/mL after previously reaching viral suppression ('blip') within 12 months prior to screening is allowed, provided a subsequent viral load measurement is <50 HIV-1 RNA copies/mL (or HIV-1 RNA undetectable by a local HIV-1 RNA test) prior to screening.
- 4. Screening eGFRcr  $\geq$ 50 mL/min according to the Cockcroft-Gault formula for creatinine clearance.
- 5. Absence of history of failure on DRV treatment and absence of DRV RAMs (including V11I, V32I, L33F, I47V, I50V, I54M, I54L, T74P, L76V, I84V, L89V), if documented historical genotypes are available.
  - If no historical genotype is available, the subject can be included, provided no previous failure on DRV treatment has been documented.
- 6. Normal ECG at screening (or if abnormal, determined by the investigator to be not clinically significant).
- 7. Screening hepatic transaminases (alanine aminotransferase [ALT] and AST) ≤5 x upper limit of the normal range (ULN).
- 8. Screening direct bilirubin  $\leq 1.5 \text{ x ULN}$ .
  - Subjects with documented Gilbert's Syndrome or hyperbilirubinemia due to ATV therapy may have total bilirubin up to 5 x ULN.

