2.6.2. Per Protocol Analysis Set

An analysis based on the per protocol (PP) population will also be performed to investigate the impact of excluding subjects with major protocol violations and to evaluate the robustness of the analysis results. The PP population will include all subjects who:

- (1) are randomized into the study,
- (2) have received ≥ 1 dose of treatment in the study, and
- (3) without any major protocol deviation that is considered to potentially affect efficacy outcomes. Specific details are provided in Attachment 1.

The PP analysis set is the secondary analysis set for efficacy analysis. The per protocol (PP) set is defined as the ITT analysis set minus subjects with major protocol violations as listed in Attachment 1.

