ATTACHMENT 1: PREDEFINED MAJOR PROTOCOL DEVIATIONS-BASED ON THE CURRENT LIST

The predefined major protocol deviations of this study are described in the Protocol Deviation Criteria document. The deviations that are considered to have an (possible) impact on efficacy are a subset of the predefined major protocol deviations and are indicated with 'Yes' below (column 'Exclude from Per Protocol Analysis') and if such deviations are reported for a subject, the subject will be excluded from the PP analysis.

In addition to the table below, subjects with a baseline HIV-1 RNA value ≥ 50 copies/mL and subjects with treatment adherence $< 65\%$ (Late Switch group will use worst adherence from baseline to switch and from switch to week 96) per derivation ii will also be excluded from the per-protocol analysis set.

Sequence No.	Description	Protocol Deviation coded term (DVDECOD)	Exclude from PP
1	The subject has not been treated with a stable ARV regimen consisting of a bPI (limited to DRV or ATV with rtv or COBI, or LPV with rtv) combined with FTC/TDF only for at least 6 consecutive months preceding the screening visit.	Entered but did not satisfy criteria	Yes
2	
 • During the 12 months preceding screening while on stable ART: 
 - The subject did not have at least 1 plasma HIV-1 RNA measurement < 50 copies/mL (or HIV-1 RNA undetectable by a local HIV-1 RNA test) occurring between 12 and 2 months prior to the screening visit while on the stable ARV regimen or - The subject has a documented plasma HIV-1 RNA concentrations ≥ 200 copies/mL. or - The subject has documented more than 1 plasma HIV-1 RNA concentrations ≥ 50 copies/mL (or HIV-1 RNA detectable by a local 	Entered but did not satisfy criteria	Yes

	
HIV-1 RNA test)
 
or
 
 - The subject has at least 1 single documented plasma HIV-1 RNA concentrations ≥ 50 copies/mL and < 200 copies/mL but had no subsequent VL measurement < 50 HIV-1 RNA copies/mL at the latest 2 months prior to screening 
or
 
 • At the screening visit has HIV-1 RNA ≥ 50 copies/mL. 		
3	The subject has a history of failure on DRV treatment or any of DRV RAMs (V11I, V32I, L33F, I47V, I50V, I54M, I54L, T74P, L76V, I84V, L89V) (if historical genotypes are available)	Entered but did not satisfy criteria	Yes

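### SAP Attachment 1 item 2 requires re-suppression after a permitted blip by 2 months before screening; inclusion criterion 3 does not, so some eligible subjects would be coded as entry violators and removed from the Week 96 per-protocol set

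*SAP*

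**What the plan says.** Criterion 3 in protocol section 4.1 has two separate timing conditions.

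- **Qualifying suppressed value.** At least one suppressed measurement is needed, "occurring between 12 and 2 months prior to the screening visit while on the stable ARV regimen". This is where the 2-month limit belongs.
- **Permitted blip.** The criterion tolerates one elevation of at least 50 and under 200 copies/mL in the preceding 12 months, on this condition: "provided a subsequent viral load measurement is <50 HIV-1 RNA copies/mL (or HIV-1 RNA undetectable by a local HIV-1 RNA test) prior to screening". No 2-month limit is attached.

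SAP section 1.2 restates the blip rule with the same condition.

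SAP Attachment 1 item 2 lists several alternative ways to fail, joined by "or" conditions. One enforces the 12-to-2-month window for the qualifying value. Another concerns the blip: it is a deviation if no later value below 50 copies/mL was obtained "at the latest 2 months prior to screening". The whole item carries the code "Entered but did not satisfy criteria" and is marked Yes for exclusion from PP.

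The consequence is stated in Attachment 1: "if such deviations are reported for a subject, the subject will be excluded from the PP analysis". SAP section 2.6.2 agrees, with the PP set "defined as the ITT analysis set minus subjects with major protocol violations as listed in Attachment 1". SAP section 3.8 tabulates all major deviations and the proportion of subjects excluded from PP.

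**The concern.** The deviation list should apply the eligibility rule that sites followed. Here it applies a stricter one. A site that enrolled a subject correctly under criterion 3 would see that subject reported as entered in breach of the criteria, and the subject would leave the PP set without having deviated from the protocol. That conflicts with the purpose of the set in protocol section 11.3 and SAP section 2.6.2, which is to show what happens when subjects with major protocol deviations are removed.

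Two outputs are at stake: the accuracy of the deviation table, and the make-up of the PP set used for the key secondary endpoints at Week 96. The SAP also contradicts itself, since section 1.2 and Attachment 1 state different rules for the same subjects.

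**Working it through.** No figure in the plan depends on this rule, so there is none to reproduce. The check is to apply both rules to the same viral-load histories.

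**Rules**

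- Criterion 3, blip part: after the blip, some value below 50 at any time before screening.
- Attachment 1 item 2, blip part: after the blip, some value below 50 at 2 months before screening or earlier.

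**Histories.** These are illustrative. Months are counted back from screening. Every history has a value below 50 at screening, a suppressed value in the 12-to-2-month window and at most one blip under 200 copies/mL, so only the blip rule can separate them.

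| History | Eligible under criterion 3 | Deviation under Attachment 1 |
|---|---|---|
| A: no blip | Yes | No |
| B: blip at −6, below 50 at −3 | Yes | No |
| C: blip at −3, below 50 at −1 | Yes | **Yes** |
| D: blip at −1.5, below 50 at −0.5 | Yes | **Yes** |
| E: blip at −6, next value below 50 at −1 | Yes | **Yes** |
| F: blip at −3, no value below 50 before screening | No | Yes |

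The rules disagree on C, D and E. In each, the first re-suppressed value falls in the last 2 months before screening. History D shows that a permitted blip inside those 2 months can never satisfy Attachment 1. If the sub-bullet used criterion 3's condition, C, D and E would cease to be deviations, F would remain one, and the rules would agree on all six.

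**Possible size.** The documents give no number or timing of pre-screening blips, so the number affected cannot be computed. The following is illustration only. It assumes the planned arm sizes of 734 and 367, a 4% rebound rate (the Week 48 planning value, not a Week 96 rate) and 5 subjects removed from the group in question.

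- Group of 734: 0.04 × 734 = 29.36 expected rebounders.
  - None of the 5 rebounds: 29.36 / 729 = 4.03%.
  - One of the 5 rebounds: 28.36 / 729 = 3.89%.
  - All 5 rebound (extreme): 24.36 / 729 = 3.34%.
- Group of 367: 0.04 × 367 = 14.68 expected rebounders.
  - None of the 5 rebounds: 14.68 / 362 = 4.06%.
  - One of the 5 rebounds: 13.68 / 362 = 3.78%.
  - All 5 rebound (extreme): 9.68 / 362 = 2.67%.

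The PP rate moves materially only if most of the excluded subjects rebound.

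**The case against.** **A PP set may be stricter than eligibility.** Protocol section 11.3 leaves PP details to the SAP and itself excludes properly enrolled subjects whose baseline HIV-1 RNA is 50 copies/mL or more. A deliberate 2-month rule could be defended on the same lines. This stands, but it does not rescue the item as written. The item does not present itself as an added PP restriction; it codes the subject as having failed the entry criteria, which is untrue.

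**The consequence is limited.** This also stands. SAP sections 1.3 and 4.4.1 make the Week 96 analysis descriptive, with no hypothesis tested. Of the PP set, SAP section 2.6.2 says: "The PP analysis set is the secondary analysis set for efficacy analysis". The ITT set is untouched. The rule depends on a pre-randomisation characteristic and applies alike to both arms, so there is no evident reason for differential bias.

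**Exclusion depends on reporting.** Subjects are removed only if the deviation is reported, and Attachment 1 refers to a Protocol Deviation Criteria document that was not supplied. The text shows what would happen if the item were followed, not that anyone was misclassified.

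**A stronger reading about rebound risk.** A reader might infer that the rule strips out the subjects most likely to rebound and so flatters the PP result. The documents do not support this. They give no rebound rates by pre-screening blip. The SAP uses screening, baseline or pre-dose viral load of 50 or more as a subgroup (section 2.7.1) and as a Cox model term (section 4.6.2), but neither addresses historical blips before screening. A link is plausible but remains an assumption.

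**Conclusion.** The mismatch is real, and nothing in either document resolves it. The 12-to-2-month window does not explain it, because item 2 already enforces that window in a separate sub-bullet.

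The affected group is narrow: subjects with one permitted blip whose first re-suppressed value came less than 2 months before screening. It would be wrong to read this as eligible subjects in general being dropped. How many there are is unknown and probably few. What is affected is the major-deviation table and the Week 96 PP set.

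A reader might also carry the point over to the PP robustness check on the Week 48 noninferiority result. That cannot be done from these documents: this SAP does not analyse the primary endpoint, and the Week 48 SAP was not supplied.

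The conclusion rests on the item being applied as written. It is a wrong rule rather than a missing detail, so it should be corrected even though its numerical effect is likely to be small.

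**What to change.** Rewrite the end of the blip sub-bullet in Attachment 1 item 2 so that a deviation arises only when criterion 3's condition is not met, namely "provided a subsequent viral load measurement is <50 HIV-1 RNA copies/mL (or HIV-1 RNA undetectable by a local HIV-1 RNA test) prior to screening". Two things matter in the wording: remove the 2-month limit, and keep the alternative of an undetectable result on a local test. Without that alternative, a subject re-suppressed on a qualitative local result would still be eligible but excluded.

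Then recheck every subject already flagged under the current wording, correct the deviation table and PP membership where needed, and bring the Protocol Deviation Criteria document into line if it contains the same text.

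If the 2-month rule is deliberate, keep it as a separately listed and justified PP restriction, alongside the baseline viral-load and adherence exclusions that Attachment 1 already places outside the table, and do not code it as an entry-criterion violation.

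The cost is one sentence in a SAP attachment and a review of the flagged subjects. No new data, change in sample size or change to the ITT analysis is needed.

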4.6.1. Definitions

Virologic Rebound

Virologic rebound is defined as:

- subjects who show confirmed HIV-1 RNA $\geq 50/20/200$ copies/mL from the reference up to, and including Week 96,
- subjects who discontinued prematurely (irrespective of reason) for which the last available (single) HIV-1 RNA value on treatment was $\geq 50/20/200$ copies/mL.
- any subject with last available on-treatment HIV-1 RNA $\geq 50/20/200$ copies/mL at the study cut-off of Week 96 (i.e., any last viral load [re]test having occurred no later than 6 weeks after Week 96)

All other situations are considered non-rebounders.

Snapshot approach (applying 20/50/200 copies/mL as threshold)

The Snapshot approach will classify subjects into 3 outcome categories: “virologic success”, “virologic failure” and “No viral load data”. Several subcategories of the outcome will also be presented in the analysis and are shown below. The categories below are mutually exclusive such that a subject will be included in one (sub)category. If a subject discontinues in the time window but also has an HIV-RNA value in the time window then the viral load data will be used to classify the subject’s category.

- Virologic success:
 - Last available HIV RNA $< 20/50/200$ copies/mL in the Week 96 visit window (Week 90-102)
- Virologic failure:
 - Last available HIV RNA $\geq 20/50/200$ copies/mL in the Week 96 visit window (Week 90-102)
 - Virologic failure leading to discontinuation

- Discontinued due to other reason (i.e. other than AE/death or virologic failure) and last available HIV-RNA $\geq 20/50/200$ copies/mL
- No viral load data in the Week 96 visit window
 - Discontinued due to AE/death (subjects will be classified in this category if discontinued prior to Week 96 window regardless of HIV-RNA level)
 - Discontinued due to other reason (i.e. other than AE/death or virologic failure) and the last available HIV RNA $< 20/50/200$ copies/mL (or missing)
 - Missing data during the Week 96 visit window but on study

The following threshold criteria are considered:

- < 20 : HIV RNA below 20 copies/mL (target not detected or target detected)
- < 50 : HIV RNA below 50 copies/mL
- < 200 : HIV-RNA below 200 copies/mL

Imputations for missing values

The following imputation method is used to calculate **virologic response** at a given time point:

- observed case: subjects with a missing value are disregarded in the analysis for that time point.

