4	The subject uses disallowed concomitant therapy specified in the protocol	Entered but did not satisfy criteria	Yes
5	The subject has any known allergies to the excipients of the D/C/F/TAF tablet, but the subject was randomized.	Entered but did not satisfy criteria	Yes

6	The dose of Investigational treatment arm (D/C/F/TAF tablet) or the active control arm (maintain current regimen consisting of a bPI with FTC/TDF) was temporarily not according to protocol for more than 4 consecutive weeks.	Received wrong treatment or incorrect dose (missed dose or extra dose)	Based on >4 weeks period. In that case classified as major and excluded from PP
7	The intake of Investigational treatment arm (D/C/F/TAF tablet) or the active control arm (maintain current regimen consisting of a bPI with FTC/TDF) was interrupted for toxicity reasons for more than 4 consecutive weeks.	Received wrong treatment or incorrect dose (missed dose or extra dose)	
8	The intake of Investigational treatment arm (D/C/F/TAF tablet) or the active control arm (maintain current regimen consisting of a bPI with FTC/TDF) was interrupted for non-toxicity reasons for more than 4 consecutive weeks, or cumulatively for more than 8 weeks.	Received wrong treatment or incorrect dose (missed dose or extra dose)	
9	The subject takes disallowed medication as defined per protocol.	Received a disallowed concomitant treatment	Yes (adjudication based on drug/class and duration).
10	The subject missed two or more consecutive planned visits in the trial	Other	Yes
11	Misallocation of Medkits was observed during Dosage and administration of study drug and subject treated differently than what they were randomized to for more than 4 weeks	Other	Yes
12	After achieving HIV-1 RNA <50 copies/mL, a single HIV-1 RNA value was ≥ 50 copies/mL, but a viral load retest or scheduled viral load test within 6 weeks of the previous VL result of ≥ 50 copies/mL was not collected (except for screening and baseline results)	Other	Yes
13	Subject missed the Week 96 visit.	Other	Yes
*Some sites assumed that protocol language “abnormal lab values that would lead to exclusion could be repeated once” applied also to viral load >50c/mL at screening.			

** Including subjects whose HIV-1 RNA was ≥ 50 copies/mL at screening, but had a HIV-1 RNA < 50 copies/mL at a not per protocol defined retest during the screening period and who were randomized based on the latter HIV-1 RNA.

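### SAP Attachment 1, item 13 drops a subject from the per-protocol set for missing Week 96 even when rebound has already been recorded

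*SAP*

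**What the plan says.** SAP section 2.6.2 builds the PP set by subtraction: "The per protocol (PP) set is defined as the ITT analysis set minus subjects with major protocol violations as listed in Attachment 1". Its purpose is "to evaluate the robustness of the analysis results", and its rank is stated: "The PP analysis set is the secondary analysis set for efficacy analysis".

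Attachment 1 lists the deviations and gives the rule: "if such deviations are reported for a subject, the subject will be excluded from the PP analysis". Item 13 reads "Subject missed the Week 96 visit" and is marked Yes. Other items carry limits: items 6 to 8 depend on how long dosing was off-protocol or interrupted, and item 9 is adjudicated by drug and duration. Item 13 carries none.

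SAP section 4.6.1 counts a subject as a rebounder for confirmed HIV-1 RNA at or above the threshold at any time from reference up to and including Week 96. It also counts "subjects who discontinued prematurely (irrespective of reason) for which the last available (single) HIV-1 RNA value on treatment was" at or above the threshold. A further limb covers a last on-treatment value at or above the threshold at the Week 96 cut-off.

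The Snapshot in the same section has three no-data groups. Two consist of subjects who discontinued, for an adverse event or death, or for another reason with a last value below threshold or missing. The third is "Missing data during the Week 96 visit window but on study".

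Section 4.6.2 says the key secondary endpoints are repeated on PP and leaves the list of PP outputs to the Data Presentation Specifications, which are not among the documents.

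**The concern.** A PP set should leave out subjects whose conduct in the trial could have distorted the outcome. Protocol section 11.3 gives examples: earlier darunavir failure, interfering medication and poor adherence. Missing one late visit is different. It affects whether a Week 96 value exists, but not a rebound already on record.

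The route from rebound to a missed visit is a real one. Protocol section 9.3 allows a subject with confirmed rebound and no detected resistance to continue study drug. Such a subject can rebound early, remain in the trial and miss Week 96. Item 13 then deletes an observed event from the analysis meant to test robustness. If rebounders are the people who tend to miss visits, the exclusion depends on the outcome, and PP would look better than ITT for a reason unrelated to protocol adherence.

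**Working it through.** **Applying the text to individual records**

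1. Initial switcher, confirmed rebound at Week 36, stays on drug, misses Week 96. ITT: rebounder under the first limb of the definition. PP: absent. This holds however the word missed is read. For late switchers, rebound is counted from the switch (sections 2.9 and 4.4.2.1), so a Week 36 event does not count for them. A confirmed rebound after the switch followed by a missed Week 96 visit behaves the same way.
2. On study, suppressed at Week 84, misses Week 96, no value in Weeks 90 to 102. ITT Snapshot: no data, on study. PP: absent.
3. Discontinues at Week 60 with a last value at or above threshold. ITT: rebounder under the second limb. PP: absent only if discontinuation is reported as a missed visit, which the SAP does not say.

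**Size for rebound**

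The documents give no number of missed Week 96 visits and no PP figure to reproduce, so this is an illustration. Inputs: N = 734 (planned D/C/F/TAF arm) and a 4% rebound rate (SAP section 1.4, a Week 48 design assumption borrowed here). As background, the plan's own power reproduces from these inputs: SE = √[0.04 × 0.96 × (1/734 + 1/367)] = 0.01253; 0.04/0.01253 − 1.96 = 1.23; power 0.891 against the stated 89%.

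Rebounders R = 0.04 × 734 ≈ 29, so the ITT rate is 29/734 = 3.95% (Clopper-Pearson 95% CI 2.66% to 5.63%). With M subjects missing Week 96, of whom k are rebounders, the PP rate is (R − k)/(N − M). It falls below ITT only when k/R exceeds M/N.

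| Assumed rebounders dropped, k | M = 37 (5%) | M = 73 (10%) |
|---|---|---|
| None | 29/697 = 4.16% | 29/661 = 4.39% |
| About in proportion (1; 3) | 28/697 = 4.02% | 26/661 = 3.93% |
| 7 (about 25%) | 22/697 = 3.16% | 22/661 = 3.33% |
| 14 (about 50%) | 15/697 = 2.15% | 15/661 = 2.27% |

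**Size for the Snapshot**

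Assume an invented ITT split of 734: 662 success, 5 failures in window, 6 failures by discontinuation, 45 discontinued without data, 16 on study without data. ITT success is 662/734 = 90.2%.

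- If item 13 catches only the 16 on-study subjects: 662/718 = 92.2%.
- If it also catches all discontinuers: 662/(662 + 5) = 99.3%.

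The gap of about 7 points between the last two figures comes entirely from how one undefined word is read.

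**The case against.** The strongest reply is that the effect is small and visible. PP is secondary, Week 96 tests no hypothesis (SAP sections 1.3 and 4.4.1), and the ITT results and the Week 48 primary analysis are untouched. Section 3.8 tabulates major deviations by arm and the proportion excluded from PP. Leaving out subjects with no assessment at the analysis time point is also a recognised PP choice. The Protocol Deviation Criteria document, which is not supplied, may define a missed visit. All of this stands and limits the weight of the point. It does not remove record 1: a deviation table does not show how many excluded subjects had rebounded.

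A reader might go further in two ways that the documents do not support.

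- That the PP Snapshot no-data groups are empty by construction, with success rising by roughly the whole no-data share. Two of the three groups are discontinuers, whom the SAP treats separately from a missing visit: section 2.5.1 has different end-date rules for each, and section 3.5 counts discontinuers on their own. Even the on-study group is defined by having no viral load in Weeks 90 to 102, not by attendance. Someone who attends without a usable sample, or outside the window, still falls in it.
- That PP rebound is biased down by construction. The table shows no fall when missing the visit is unrelated to rebound, and a slightly higher rate when no rebounder misses it.

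**Conclusion.** The point holds in limited form. Item 13 removes subjects whose rebound is already established, because it has no exception for them and acts on the whole subject. The direction of the effect is conditional: the PP rebound rate is understated only if rebounders miss Week 96 more often than others. Under assumed missingness of 5% to 10%, with 7 to 14 of 29 rebounders dropped, 4.0% in ITT becomes about 2.2% to 3.3% in PP. The upper part of that loss is hard to reach if only subjects still on study are caught, since rebounders who discontinue would then stay in PP.

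On the on-study reading, the Snapshot loses most of its on-study missing group and nothing else. If discontinuers were counted as well, discontinuation-based rebounders and most no-data subjects would also leave PP. The SAP should settle which reading applies. Whether a PP Snapshot is produced at all depends on the Data Presentation Specifications. The consequence is confined to a secondary, descriptive robustness analysis, but the correction is cheap enough that it should be made.

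**What to change.** Reword item 13 along these lines: *Subject still on study treatment missed the Week 96 visit and had not already met the virologic rebound definition.* State in Attachment 1 that early discontinuation is not a missed visit under items 10 and 13. Report the number excluded under item 13 by treatment group and by rebound status in ITT, so that any link between exclusion and outcome can be seen.

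Deleting item 13 altogether is an option but not required; whether PP should demand a Week 96 assessment from subjects who have not rebounded is a matter of judgement.

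The cost is a short SAP wording change and a rerun of the PP flag. The small downside is that PP keeps a few subjects without a Week 96 value.
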